Blood pressure will be measured according to standards set by the American Heart Association (AHA) using an automated monitor. Participants will be sitting for a minimum of 10 minutes before blood pressure is taken. Two readings will be taken and an average of the two will be used for data analysis. Participants presenting with a reading 140/90 or higher will be given a letter recommending them to consult with their primary care doctor at their earliest opportunity. An ambulance will be called for participants presenting with a reading of 220/120 or higher.

Participants will receive an e-mail immediately after the baseline visit which will include the survey link. Additionally, an e-mail will be sent providing further instructions for 2nd and 3rd dietary recalls. Participants ineligible after the baseline visit will be notified by the research assistant or coordinator that they do not meet criteria for the study. This will be communicated via e-mail if the reason is not sensitive (i.e. inability to get medical clearance, taking exclusionary medication, or expressing a preference for either condition). If the reason is sensitive (i.e. high depression score, suicidal ideation, presence of BED) staff will call them to let them know. In the conversation, staff will let them know that when depression is very high, it's best to focus on that first rather than focusing on multiple things such as depression plus weight loss. In the conversation for BED, we will let them know that the DPP is not an appropriate intervention because we don't provide psychological help in the intervention, and receiving professional help, specifically cognitive behavioral therapy, will be more beneficial to them. We will offer to send a list of local resources to these participants. If suicidal ideation is present, the program director will call to assess safety and suggest professional help if needed.

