Participants will complete a telephone screening, an in-person baseline, and an online webinar (described above). Eligible participants will then be randomized to one of two 12-month weight loss interventions: online (Get Social) or in-person (Traditional). Follow-up assessments will occur at 6- and 12-months.

Randomization: Randomization will take place after the baseline procedures are complete once we've determined eligibility. Participants will be randomized to the Get Social or the Traditional condition. We will randomize 36-40 participants for each recruitment wave, for a goal of approximately 18 per condition. Participants will be randomized 1:1 to the two study conditions in randomly permuted blocks of size 4 and 6 using the ralloc program in Stata Randomization and will be stratified by gender (male vs. female) and baseline BMI (27.0-34.9 vs. 35.0-45.0). The randomization list was generated at the start of the study before randomization. The list is managed by the program director. Once a participant has been determined to be eligible, the program director will assign each participant to the next open assignment on the list. The program director will then tell the research assistant who will reach out to participants to inform them via e-mail of the condition assignment.

Orientation-Visits:

- Traditional participants: This in-person group will last 1 hour and will include training on The first session of the intervention will be extended from 1.5 hours to 2 hours in order to provide time for the orientation which will cover: -My Fitness Pal, an overview of their participation, and study goals. My Fitness Pal is an app that can be used to track diet and physical activity. It can be used on a computer or mobile app. Participants will receive their study goals for weight loss (1-2 lbs. per week), diet, and physical activity. The weight loss goal is approximately 7% weight loss over a 12 month period. This orientation may be completed on an individual in-person basis or phone for people unable to attend the group, though this option won't be encouraged. The weight loss goal is provided in the My Fitness Pal app. –The orientation group is led by the interventionist, a post-doctoral fellow, and a research assistant. and research assistants.

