Inclusion/Exclusion Criteria: [List ALL inclusion and exclusion criteria. Any proposed exclusion criterion based on gender (women of childbearing potential), age, or race must include justification for the exclusion. Describe the conditions under which participants may be removed from the study, i.e., noncompliance with study rules, study termination, etc.]

Smartphone users ages 18-65 with a BMI 27-45 will be recruited for this study. Participants must log into a social media platform on a daily basis and engage (like, reply, post) at least 4 days per week.

Age justification: Weight loss interventions intended for ages outside of the range (<18 or >65) require individualized attention from a physician and will not be appropriate to use the DPP.

Participants will be excluded if they:

- 1. Do not have a smartphone;
- 2. Are unable to get medical clearance from their PCP;
- 3. Have plans to move during study;
- 4. Are not interested in losing weight;
- 5. Have Type 1 Diabetes or uncontrolled Type 2 Diabetes (as determined by PCP);
- 6. Have medical conditions that would prevent increasing physical activity or making dietary changes;
- 7. Are pregnant/lactating or plans to become pregnant during study;
- 8. Are currently taking medication affecting weight;
- 9. Currently participating in a clinical weight loss program to assist them with weight loss (e.g. Weight Watchers, Sparkpeople, etc);
- 10. Unable to walk at least ¹/₄ mile unaided without stopping;
- 11. Experienced a weight loss of 5% or more in past 3 month;
- 12. A history of/or plans on having bariatric surgery;
- 13. Did not complete the baseline measures;
- 14. Not willing to use Twitter, or if a current Twitter user, not willing to create an new account specifically for study purposes;
- 15. Participated in another weight loss study under the direction of the PI of this study;
- 16. Current smoker (smokes 3 or more cigarettes per day);
- 17. Unavailable to attend weekly group meetings;
- 18. Prefers one condition over another;
- 19. Score of 30 or higher on the BDI or endorsement of 2 or 3 on BDI #9 indicating suicidal thoughts;
- 20. Presence of binge eating disorder;
- 21. Did not complete the orientation webinar;
- 22. Are unable to provide consent due to mental illness or a cognitive impairment;
- 23. Does not speak English; or
- 24. Are a prisoner

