To be able to actively participate in the study, participants must be adults without impaired decision making ability that are able to speak and read English. The consent process will include a discussion of the participants understanding of what participating in research means including their rights as a research participant, the protocol, as well as risks and potential benefits to participating in the study. If research personnel obtaining consent believes there is a concern regarding a participant understanding participation will be discussed with the program director who will determine whether to exclude the participants on this basis.

Parent/Guardian Permission and Assent: [If enrolling children, state how many parents/guardians will provide permission, whether the child's assent will be obtained and if assent will be written or oral. Provide a copy of the script to be used if oral assent will be obtained.]

N/A

Documentation of Consent: [Specify the forms that will be used for each participant population, i.e., adult consent form, surrogate consent form, child assent form (written form or oral script) or an information sheet. Copies of all forms should

be attached to this application in the same format that they will be given to participants (templates and instructions are available on the IRB website).]

Adult consent form will be used for the study participants and an information sheet for the interventionists.

Waiver or Alteration of Consent: [The IRB may waive or alter the elements of consent in some minimal risks studies. If you plan to request either a *waiver of consent* (i.e., participants will not be asked to give consent), an *alteration of consent* (e.g., deception) or a *waiver of signed consent* (i.e., participants will give consent after reading an information sheet), please answer the following questions using specific information from the study:]

Waiver (i.e. participants will not be asked to give consent) or alteration of consent (e.g. use of deception in research):

- *Why is the study considered to be minimal risk?*
- How will the waiver affect the participants' rights and welfare? The IRB must find that participants' rights are not adversely affected. For example, participants may choose not to answer any questions they do not want to answer and they may stop their participation in the research at any time.

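### The program director holds the pre-generated allocation list, makes the assignments and has a partial role in entry, and no step is described that conceals upcoming assignments from that person

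*Protocol*

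**What the plan says.** Protocol, Study Design, Randomization: allocation is 1:1 in permuted blocks of 4 and 6, stratified by gender and two baseline BMI bands, with 36-40 participants randomized per wave. On the list: "The randomization list was generated at the start of the study before randomization". On who holds it: "The list is managed by the program director". On who uses it, once eligibility has been determined: "the program director will assign each participant to the next open assignment on the list". The program director then tells the research assistant, who informs the participant. The paragraph does not say who generated the list.

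Protocol, Capacity to Consent: where consent staff doubt a participant's understanding, "participation will be discussed with the program director who will determine whether to exclude the participants on this basis".

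Protocol, Data Security: the program director controls the database and surveys and grants staff access.

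The SAP does not mention randomization or concealment.

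**The concern.** Allocation concealment means that nobody who can influence whether or when a person enters knows the next assignment. Here one role holds the complete list, fills its slots and has at least one say over exclusion. If that person can read ahead, the next assignment could affect, even unintentionally, whether a doubtful candidate is kept or which of two waiting candidates is placed first.

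The arms would then differ in prognosis for reasons that the analysis cannot see. The arms cannot be masked, and the primary comparison is judged against a margin of 2 percentage points. Selection that favoured Get Social would therefore act directly on the non-inferiority conclusion.

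**Working it through.** **1. What is stated, function by function.**

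| Function | Who, per the Protocol |
|---|---|
| Generates the list | Not stated |
| Holds the list | Program director (Randomization) |
| Makes the final eligibility decision | Not stated |
| Decides exclusion when understanding is in doubt | Program director (Capacity to Consent) |
| Fixes the order in which eligible people are placed | Not stated |
| Places each person on the list | Program director (Randomization) |
| Controls the database | Program director (Data Security) |
| Conceals upcoming slots | No step described |

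REDCap is described for data entry, management and tracking, not for releasing assignments.

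**2. Do the random block sizes protect?** Only against guessing. In a simulation of 20,000 sequences, with blocks of 4 and 6 assumed equally likely, someone who knew only the past assignments in a stratum guessed the next one correctly 69% of the time. Someone who can read the list knows it 100% of the time.

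**3. Could several candidates be waiting at once?** Gender by BMI gives 2 x 2 = 4 strata. A wave of 36-40 averages 36/4 = 9 to 40/4 = 10 per stratum if strata fill equally, which is an assumption. So it is possible, and no rule says who goes first. The wave size is a target, however, and does not show that a queue formed.

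**4. Scale for judging any bias.** Inputs from Justification of Sample Size: SD 5.5%, margin 2%, alpha 0.05 (sidedness not stated), power 90%, 131 per arm, 20% attrition.

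- The plan's own figure, by normal approximation with one-sided alpha 0.05: n = 2 x (1.645 + 1.282)² x 5.5² / 2² = 129.6, so 130 per arm. The noncentral-t version gives 131 (power 0.902). Then 131/0.8 = 163.75, so 164 per arm and 328 in total. The plan's numbers reproduce.
- Standard error of the difference: 5.5 x √(2/131) = 0.68 points.

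**5. Illustration with assumed inputs only.** Suppose a share f of one arm is replaced by people whose expected weight loss is g points better. The shift is b = f x g. At a true difference exactly at the margin, the chance of wrongly declaring non-inferiority is 1 − Φ(1.645 − b/0.68).

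| f | g (points) | b (points) | False non-inferiority |
|---|---|---|---|
| none | none | 0 | 5% |
| 5% | 2 | 0.10 | about 7% |
| 5% | 5 | 0.25 | about 10% |
| 10% | 5 | 0.50 | about 18% |
| 20% | 5 | 1.00 | about 43% |

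Neither f nor g comes from the documents. The table shows how the error rate would respond to a bias of a given size. It does not estimate a bias in this trial.

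**The case against.** The strongest reply is that the procedure is sequential and the director's stated power over entry is narrow. Eligibility is settled before assignment, the next open slot is used, and the research assistant learns the condition only afterwards. The one exclusion given to the director concerns understanding at consent. Consent takes place at the start of the baseline appointment, before the remaining baseline items and the webinar are complete. A person's eventual slot would rarely be known then. Inclusion and exclusion data also go to outside safety officers twice a year and after each wave.

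Much of this stands, and it limits the point. Three stronger readings are tempting, and the documents do not support them:

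- **That the director rules on other exclusions.** For suicidal ideation, the Baseline Visit text says only that "the program director will call to assess safety and suggest professional help if needed". That is a safety call; the exclusion itself follows a fixed depression-inventory threshold. The criterion "Prefers one condition over another" is not assigned to the director anywhere. Study staff review the randomization agreement, which the participant completes and signs.
- **That the director is known to see upcoming slots and to choose the order.** Both are inferences from managing the list and filling it. The text neither states nor excludes either.
- **That allocation was in fact subverted.** Nothing in the documents suggests it.

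What the reply does not supply is a concealment step. Putting eligibility before assignment does not hide the next assignment while eligibility is being settled. The safety officers' reports are only a partial check, because the director helps to produce them and placement order is not listed among their contents.

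**Conclusion.** The concern holds as a gap in the described procedure. The program director holds the list, makes the assignments and has a partial role in entry, and nothing in either document shows that upcoming assignments were hidden from that role. The documents give no evidence of bias, and its size and direction cannot be estimated from them. The illustrative error rates rest wholly on assumed inputs.

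The gap is worth closing because it touches the basic protection of the primary comparison and is cheap to remove. Whether it can still be closed is uncertain. The Protocol places waves 7-9 in the future, but the SAP is dated 26 February 2021 and describes problems with participant cost data in the past tense. This suggests, without saying so, that randomization may be complete. If it is, only disclosure remains.

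**What to change.** **For any wave not yet randomized** (7-9, according to the Protocol's study population and Intervention Phase text):

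1. Someone with no enrolment role, such as the study statistician, generates a new list with the same block sizes and strata. Transferring the present list would hide nothing from a person who has already held it.
2. That person holds the list, or it is loaded into REDCap with the program director's access to the allocation table removed. Because the director controls the database, REDCap release alone does not conceal anything.
3. Each assignment is released only after a time-stamped eligibility lock, in lock order.

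**For waves already randomized**, including 7-9 if they are complete: report who generated the list, who could see it, and how placement order was set.

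**Cost:** a one-time set-up and a separation of access rights. Sample size, allocation ratio, blocks and strata do not change.

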As PI, you are responsible for taking reasonable steps to assure that the participants in this study are fully informed about and understand the study. Even if you are not targeting participants from "Special Populations" as listed on page 4, such populations may be included in recruitment efforts. Please keep this in mind as you design the Consent Process and provide the information requested in this section.

Consent Setting: [Describe the consent process including who will obtain consent, where and when will it be obtained, and how much time participants will have to make a decision. Describe how the privacy of the participants will be maintained throughout the consent process. State whether an assessment of consent materials will be conducted to assure that participants understand the information (may be warranted in studies with complicated study procedures, those that require extensive time commitments or those that expose participants to greater than minimal risk).]

The consent process will take place at the beginning of the baseline appointment. Ample time will be allowed for discussion or questions. Consent will be obtained by research assistants/coordinators trained in the consent process. To ensure that participants are given enough time as needed to review the consent form, they will be emailed the consent form prior to the baseline appointment.

The interventionists will receive an online survey at the 6-month time point of each wave. An information sheet appears on the first page in place of a signed consent form. They will as much time as needed to review the information sheet and email/call staff for questions. They may also decide not to complete the survey.

Capacity to Consent: [Describe how the capacity to consent will be assessed for participants with limited decisionmaking capacity, language barriers or hearing difficulty. If a participant is incapable of providing consent, you will need to obtain consent from the participant's legal guardian (please see the IRB website for additional information).]

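### One-at-a-time assignment, disclosed to research assistants who also work at baseline, lets staff who track it guess the next arm up to 69% of the time; allocating a whole wave at once would remove most of this

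*Protocol*

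**What the plan says.** Under Study Design, Randomization, the protocol has participants "randomized 1:1 to the two study conditions in randomly permuted blocks of size 4 and 6", stratified by gender and by baseline BMI (27.0–34.9 or 35.0–45.0). The list was generated in advance and the program director holds it. Allocation is described person by person: "Once a participant has been determined to be eligible, the program director will assign each participant to the next open assignment on the list". Then: "The program director will then tell the research assistant who will reach out to participants to inform them via e-mail of the condition assignment". The same paragraph says that each recruitment wave randomises 36–40 people.

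The same staff group appears at baseline. Under Consent Setting: "Consent will be obtained by research assistants/coordinators trained in the consent process". Under Screening Procedures: "Participants ineligible after the baseline visit will be notified by the research assistant or coordinator that they do not meet criteria for the study". Research assistants also lead the individual orientation for Get Social participants. For the other baseline tasks, including review of the randomization agreement, the protocol says only that study staff do them.

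Exclusion 18 is "Prefers one condition over another". It draws on a checklist that the participant completes and signs, and on baseline survey items about each condition.

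Neither document masks staff, keeps screening staff from past assignments, or says that assignments are held until a wave closes.

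**The concern.** Holding the list securely does not stop staff inferring the next arm from assignments already released. Permuted blocks return to balance, so within a stratum the arm that is behind is more likely to come next. Staff who know the candidate's gender and BMI, and the earlier assignments in that stratum, have a better-than-even guess while the candidate's entry is still open.

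A guess matters only if it changes who enters or in what order. Two places leave some room: an ambiguous answer about preference for a condition, and how fast a candidate is moved through the remaining baseline steps. If promising candidates entered more readily when Get Social was expected next, the arms would differ in prognosis at entry. In a non-inferiority trial, a tilt in that direction raises the chance of wrongly declaring non-inferiority; a tilt the other way costs power.

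**Working it through.** **Inputs from the protocol.** Ratio 1:1; blocks of 4 and 6; four strata (2 × 2); N = 328; nine waves of 36–40; SD 5.5%; margin 2%; 131 evaluable per arm; alpha 0.05. The mix of block sizes is not stated; I assume equal numbers and show the range.

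**The plan's own figure.** No guess rate is stated, so there is none to reproduce. The sample size does reproduce: with one-sided alpha 0.05, SD 5.5, margin 2 and 90% power, the normal formula gives 130 per arm, and t-based power at 131 is 90.2%. Also 131/0.8 = 163.75, so 164 per arm and 328 in total. The one-sided 5% level is therefore used below.

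**Ceiling on the guess rate.** Rule: guess the arm that is behind in the stratum, and toss a coin when tied. Expected correct guesses in a block of 2m are m + ½ × (2^(2m)/C(2m,m) − 1).
- Block of 4: 2 + ½ × (16/6 − 1) = 2.833, so 2.833/4 = 70.8%.
- Block of 6: 3 + ½ × (64/20 − 1) = 4.10, so 4.10/6 = 68.3%.
- Equal numbers of each: (2.833 + 4.10)/10 = 69.3%.

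Full enumeration of both block sizes agrees, and simulation of the whole trial gives 69%. The rule does not need the block sizes, because imbalance returns to zero after either.

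**Below the ceiling** (simulation, same blocks; these scenarios are assumptions):

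| What staff know, or what intervenes | Correct guesses |
|---|---|
| Track only the current wave | 62% |
| Ignore strata | 60% |
| Miss 10% of past assignments | 59% |
| Miss half of past assignments | 54% |
| One same-stratum assignment between judgement and allocation | 59% |
| Two | 56% |
| Three | 52% |
| Five | 50% |
| Whole wave released together | 53–54% |

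**Illustrative bias.** Let q be the share of entries influenced. Favoured and unfavoured candidates differ by one SD (5.5 points), and all influence favours Get Social. The documents support none of these three assumptions. Then η = q × 5.5/2, bias = 2η(2p − 1), SE = 5.5 × √(2/131) = 0.680, and one-sided error at a true difference of −2% is 1 − Φ(1.645 − bias/SE). At q = 10%, 2η = 0.55.
- p = 0.693: 0.55 × 0.386 = 0.21 points; error 1 − Φ(1.645 − 0.312) = 9.1%.
- p = 0.59: 0.55 × 0.18 = 0.10 points; error 1 − Φ(1.645 − 0.146) = 6.7%.
- p = 0.52: 0.55 × 0.04 = 0.02 points; error 5.3%.
- p = 0.54 (whole-wave release): 0.55 × 0.08 = 0.04 points; error 5.7%.

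At p = 0.693, q = 5% gives 0.11 points and q = 20% gives 0.42 points.

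**The case against.** The strongest reply is that this is conventional practice: a pre-generated list held by one person, mixed block sizes, and assignment only after eligibility is settled. Some predictability remains in any open trial with permuted blocks. That is fair, and it is why the change is offered as optional. It does not remove the mechanism, since the next candidate is still being judged after earlier assignments are known.

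Several limits stand in full:
- **Timing.** The preference agreement is reviewed at the baseline visit. Medical clearance, the survey, two home dietary recalls and a webinar also have to be completed. With a wave in the pipeline together, others in the same stratum may be allocated in between, and the guess decays quickly.
- **Release.** A reader might infer that each assignment reaches research assistants at once. The text gives the order of steps but not the interval, and does not exclude release in batches.
- **Who decides.** A reader might infer that research assistants judge eligibility. The protocol has them obtain consent and give notice of ineligibility; it does not say that they decide it. The preference exclusion rests partly on the participant's own checklist and survey answers.
- **Safeguards.** A reader might infer that nothing planned could detect or correct the problem. Both documents compare baseline characteristics by condition and adjust for those that differ, visits are audio recorded with a 10% sample reviewed, and the monitoring board reviews inclusion and exclusion. The adjustment reaches measured imbalance only, not an unrecorded impression of motivation.

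**Conclusion.** The point holds as a modest, avoidable weakness. As written, the procedure allows staff who track assignments to guess the next arm up to 69% of the time (68.3–70.8% over any mix of the two block sizes). With incomplete tracking, or one to three intervening same-stratum assignments, about 52–62% is the more plausible range. It would be wrong to read 69% as the trial's actual rate, or to conclude that selection has occurred: nothing in the documents shows staff tracking assignments or acting on them.

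The size and direction of any bias are unknown. The illustration of 0.10–0.21 points (5–11% of the 2% margin), with error of about 7–9% instead of 5%, covers guess rates of 59–69%. It depends wholly on 10% of entries being influenced, a one-SD contrast and influence all in one direction; at a 52% guess rate it nearly vanishes.

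**What to change.** For waves not yet randomised, replace the person-by-person rule with a wave-level step:
1. Close and lock the wave's eligibility list.
2. Allocate all 36–40 participants in one run from the existing list, in a fixed order within strata (for example by study ID).
3. Release assignments to research assistants only after that.

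The list, strata and 1:1 ratio stay as they are. The guess rate falls to about 53–54%; what remains comes from blocks left open at the end of the previous wave. If whole-wave release is already the practice, one sentence saying so is enough. Hiding the block sizes from screening staff would not help, because the guess works without them.

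The cost is a short protocol amendment, with no extra staff or procedures. People found eligible early wait until the wave closes to learn their arm, and the Get Social individual orientations must fit between wave closure and the group orientation. The reach is limited: the protocol describes waves 1–6 as already carried out, so at most waves 7–9 could change, and the SAP's 2021 date suggests that even these may be past. For waves already randomised, the report can state how and when assignments were released.
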